Subjects who lose more than 4mm of buccal plate after extraction will be excluded from the study at this time. They will receive bone allografts and collagen membrane as a socket grafting material. The test implant that does not achieve 30 N-cm will be treated as a control implant and excluded from the study.

Post-op visits after implant and bone surgery (V5, V6, V7 if necessary)

Post-op visits will be scheduled at 14 ± 3 days, 28 ± 3 days, and varied date upon subject oral condition, if needed. The informed consent along with a review of the medical history will be checked at each visit. Clinical measurements will be taken, including: mid-facial mucosal level, papilla height and labial ridge contour. Clinical photos will be taken during the visit. The

wound will be gently debrided and disinfected. Sutures, if any, will be removed.

Additional post-op visits (V7) may be necessary for conditions that require additional care for subject safety, such as premature wound exposure, minor infection, and slower healing. They are based on per subject needs for a visit, not for every subject and will be followed as adverse events. No clinical measurements will be taken at this visit.

Management of adverse events

If the dental implant does not achieve primary stability (10-20 % of prevalence rate) due to infection or other reasons, the implant will be removed in a brief surgery. The osteotomy site will be grafted with allograft bone and covered by a collagen membrane. The wound will be closed with sutures. The participants with the abovementioned conditions will be withdrawn from the study.

Alternative treatments will be given. All adverse events will be reported.

Crown impression (V9)

The impression visit will be at 4 (+/- 1) months after the baseline surgery, depending on the healing of the bone graft and implant. The informed consent will be checked along with a review of the medical history. Any adverse events will be screened and reported. If the implant fails, it will be removed and the site will be grafted at no charge. The subjects with a failed implant will be excluded. Impressions will be taken for upper and lower jaws with alginate and silicone materials, along with a bite registration.

Crown placement (V10)

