The final crown placement will be within several weeks from the impression. The informed consent will be checked along with a review of the medical history. Any adverse events will be screened and reported. If the implant is loose then the subject will be taken out of the study. The implant will be removed and bone placed where the implant was at no charge to the subject. Their participation in the study will be over at this time.

Clinical measurements, including PES/WES, mid-facial mucosal level, papilla height, and labial ridge contour will be taken. All components to be used will be commercially available from Neobiotech. A standardized radiograph and

intraoral photos will be taken. Multiple visits may be required to assure the quality of crowns.

Crown follow-up/Final visit (V11)

One crown follow-up visit will be scheduled at 10 (+/- 2) months after the baseline surgery. A standardized peri-apical film, clinical measurements, clinical photos and impressions/bite registration will be done. The clinical measurements include probing depth, plaque index, gingival index, keratinized mucosa width, PES/WES, mid-facial mucosal level, papilla height and labial ridge contour. The informed consent will be checked along with a review of the medical history. Any adverse events will be screened and reported.

Schedule of Events

Event	Screening	CBCT scan	Pre-implant placement	Implant and bone surgery	Post-Op visit 1	Post-Op visit 2	Additional post-Op visits (if necessary) (c)	CBCT scan	Crown impression (IP)	Crown Placement	Crown follow-up/ Final Visit
	V1	V2	V3	V4	V5	V6	V7	V8	V9	V10	V11
Timeline				Baseline (BL)	14 D (+/- 3D)	28 D (+/- 3D)	Varied		4 (+/- 1) M after BL	3+ wks after IP	10 (+/- 2) M after BL
Informed consent	SIGN		X	X	X	X	X		X	X	X
Check BP, HR	X			X							
Med history review	X		X	X	X	X	X		X	X	X
Screen for adverse events				X	X	X	X		X	X	X
Eligibility Screen	X	X		X							
Impression and bite registration			X						X		X
CBCT Scan (a)		X						X			
Clinical measurements (b)			X	X	X	X				X	X
Periapical radiograph/ (S = Standardized)	X (optional)		X (S)	X (S)						X (S)	X (S)
Clinical photographs			X	X	X	X	X			X	X
Wound disinfection & suture removal (if any)					X	X	X				
Subject withdrawn by PI		Inadequate Bone		Inadequate Bone	Implant Loose	Implant Loose	Implant Loose		Implant Loose	Implant Loose	
Temp Crown for Test Group Only				X							
Bone Allograft				X							
Control Group – Temp Denture (at subject request)				X							

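### Two exit rules end participation at a study operation, and no scheduled adverse-event screen follows that operation

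*Combined protocol and SAP*

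**What the plan says.** All places are in section III (Treatment) of the combined protocol and SAP. Two rules fix the moment of exit at an operation:

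- **Implant and bone surgery (V4), exclusion paragraph.** "Subjects who lose more than 4mm of buccal plate after extraction will be excluded from the study at this time". These subjects have had an extraction, and the socket is grafted with allograft and a collagen membrane.
- **Crown placement (V10).** A loose implant is removed and bone is placed. "Their participation in the study will be over at this time".

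Two further rules involve removal and grafting but give no end date:

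- **Management of adverse events.** An implant without primary stability is taken out and the site is grafted and covered. "The wound will be closed with sutures". Then: "The participants with the abovementioned conditions will be withdrawn from the study". The next sentences read: "Alternative treatments will be given. All adverse events will be reported".
- **Crown impression (V9).** A failed implant is removed and the site grafted. "The subjects with a failed implant will be excluded".

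A fifth rule, also under V4, applies to the test arm only: "The test implant that does not achieve 30 N-cm will be treated as a control implant and excluded from the study". It describes no removal and no added operation.

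The Schedule of Events marks the adverse-event screen at V4, V5, V6, V7, V9, V10 and V11, and wound disinfection with suture removal at V5, V6 and V7. No row or footnote gives a contact for a subject who has left.

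**The concern.** The protocol recognises that wounds opening early, minor infections and delayed healing can follow surgery, and it treats them as adverse events. These problems appear days or weeks later, so a screen on the day of the operation cannot find them. Retained subjects are seen at about 14 and 28 days after the baseline operation for this reason. A subject who leaves at the operation has a fresh graft or a removal site and no scheduled occasion on which a complication would be found and recorded. The adverse-event record could then be incomplete in the subjects whose surgery went least well.

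**Working it through.** The check compares the exit rules with the schedule. The plan states no figure for this point, so there is none to reproduce.

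**1. Exit for plate loss at V4.** The adverse-event screen at V4 takes place on the day of surgery. The next screens and the first wound checks are at V5 (14 ± 3 days) and V6 (28 ± 3 days). The exclusion takes effect during V4. Scheduled screens after the operation: 0. Scheduled wound checks after it: 0.

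**2. Exit for a loose implant at V10.** The V10 screen records the loose implant itself. The only later screen in the schedule is V11, which the subject does not reach because participation has ended. The fixed wound checks are timed from baseline surgery and end by day 28 + 3 = 31. V10 comes at least 3 weeks after an impression visit that is itself at 4 ± 1 months, so those checks are long past. Scheduled screens after the removal: 0. Scheduled wound checks after it: 0.

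**3. No primary stability.** When these subjects leave is not settled. The V4 section has stability assessed at placement, and the patient-selection section allows a screen failure until the implant is placed and judged stable; both point to V4. The withdrawal row of the Schedule lists only inadequate bone at V4 and a loose implant from V5 on. The text also attaches a general reporting promise to this group. The result is probably the same as in step 1 or 2, but the wording does not establish it.

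**4. Failed implant at V9.** Removal and grafting are followed by exclusion, with no end date. If exclusion means what it does at V4, V10 and V11 fall away and no screen follows the removal. The text does not say so outright.

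**5. Test implant below 30 N-cm.** No second operation is described. The rule matters here only because these subjects also had V4 surgery and would benefit from V5 and V6.

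**6. Is the proposed slot workable?** For a removal at V5, V6 falls nominally 28 − 14 = 14 days later. With the visit windows, the gap runs from 25 − 17 = 8 days to 31 − 11 = 20 days. V6 can therefore serve as the post-removal check for a removal at V5.

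**The case against.** The strongest reply is that much of this is inference from silence. No sentence says that excluded subjects skip V5 and V6, and the post-operative visits are described with no exception for them. For subjects without primary stability, the promise to give alternative treatment and report all adverse events comes directly after the withdrawal sentence. As-needed visits also exist: "Additional post-op visits (V7) may be necessary for conditions that require additional care for subject safety". The events that trigger an exit are themselves reported. The consent pages and the case report form are not available, and follow-up after exit may be described there.

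Part of this stands. It is why the firm claim covers only the two rules that end participation at the operation, where the text is explicit. For those two, a general duty to report sets no occasion for detection. The as-needed visit responds to a problem already known, and the text does not say that it stays open to subjects who have left.

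A reader might go further in three ways that the documents do not support:

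- **All five rules cut off follow-up after an extra operation.** The 30 N-cm rule involves no added operation, and two other rules give no end date.
- **The 10–20% rate can be multiplied by 40 to count missed screens or events.** Its denominator is not stated, and the exit visit is ambiguous. The rate describes failure to achieve primary stability, not later loosening. No complication rate after grafting or removal is given.
- **Care is withheld from these subjects.** The protocol promises alternative treatment to those without primary stability and socket grafting after plate loss, and it provides grafting without charge at V9 and V10. The gap concerns recording, not treatment.

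**Conclusion.** The point holds in a narrow form. For plate loss at V4 and a loose implant at V10, the stated rules end participation at a study operation, and no scheduled adverse-event screen or wound check follows. For no primary stability and for failure at V9 the same is probable but not stated.

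The number of screens or events missed cannot be estimated, and none should be quoted. The protocol's 10–20% figure indicates only that exits of this kind are expected. The conclusion rests on the ordinary meaning of exclusion at that time and of participation being over, and on the protocol text alone.

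This is a minor safety-capture point and a cheap improvement. It changes neither the efficacy analysis nor the sample size of 40. No claim is made about the direction of any difference between arms.

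**What to change.** Add one sentence: exclusion or withdrawal ends study treatment and efficacy measurement but not safety follow-up. Then:

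- Everyone whose V4 surgery was started, whatever its outcome, keeps the adverse-event screen and the wound and suture check at V5 and V6. This includes subjects excluded for plate loss, for no stability or under the 30 N-cm rule.
- Anyone whose implant is removed after V4 has one adverse-event screen with a wound and suture check about 14 days after the removal, before participation ends. V6 can serve for a removal at V5. This should be a visit, because a telephone call cannot check a grafted wound or remove sutures.
- The V10 sentence is reworded to match, and a footnote to the Schedule of Events records the rule.

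The cost is one sentence, one footnote and one rewording. In visits, it is at most two per V4 exit, in slots that already exist, and one per later removal. The downside is a few extra visits and a slightly higher adverse-event count.

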A single center, randomized, controlled, parallel-arm study is planned to investigate esthetic outcomes after IIP + IIR in the esthetic zone. Forty adult patients who have a hopeless maxillary anterior or premolar tooth, with intact adjacent teeth will be enrolled. A signed written informed consent will be obtained after he or she has been given verbal and written information describing the nature and duration of the study. Subjects will not be screened or treated until an informed consent has been obtained. Patient information will be protected according to the privacy regulations of the federal Health Insurance Portability and Accountability Act of 1996 (HIPAA).

Enrolled patients will be randomly placed into one of two treatment groups, immediate implant placement and restoration group (IIR) or the IIP + delayed restoration group (DR). For all patients, the tooth will be extracted and an implant placed immediately. The subject will be randomly assigned before the surgery visit to either restoring the implant immediately (Test group) with a provisional crown or restoring the implant at 4 ± 1 month after implant placement (Control). Outcome analyses will be clinical and radiographic parameters to determine the esthetic outcomes of immediately restored IIP implants, in comparison to those immediately placed but restored in a delayed approach.

Study Protocol

I. Introduction

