Subjects can be considered a screen fail at any study visit prior to the surgery and up until the time that the implant is placed and deemed stable. All screen failed subjects will be replaced.

Inclusion and exclusion criteria

Inclusion Criteria

• Male or female, aged ≥ 21• A minimum dentition of 20 permanent teeth (including natural rooted teeth or dental implants; pontic of a fixed bridge is not considered a tooth)• A maxillary premolar, canine, lateral incisor or central incisor with a hopeless prognosis• Presence of adjacent teeth and enough clearance for an implant crown• Presence of sufficient bone apical to the root apex of the hopeless tooth

Exclusion Criteria

Systemic criteria:

- Current heavy smokers (>10 cigarettes per day) or heavy smoker who quit less than 1 year ago
- Pregnant or plan to get pregnant or lactating mothers
- Current alcoholism or drug abuse
- Diseases of the immune system or any medical condition that may influence the outcome (uncontrolled diabetes ($\text{HbA1c} > 7$), neurologic or psychiatric disorders, systemic infections, ...)
- Radiation therapy in the head and neck area within 3 years
- Current use of oral bisphosphonates for >3 years
- History of IV bisphosphonates use
- Other medical conditions that may contradict an implant surgery

Intraoral criteria:

- Area of study is adjacent to an existing implant
- Acute infection at/or adjacent to the extraction site (e.g., sinus tract, swelling)
- Observable gingival changes due to use of medications known to affect the periodontal status (calcium antagonists, anticonvulsives, immunosuppressants, anti-inflammatory medications...)

- Untreated deep carious lesions or defective restorations that can potentially exacerbate during the course of the experiment
- Uncontrolled periodontal disease
- Poor oral hygiene (>20% FMPS)

CBCT criteria:

- More than 4mm of buccal plate dehiscence is present on the CBCT scans

Intraoperative criteria:

- More than 4 mm of buccal plate dehiscence is present once the tooth is extracted

The screening visit (V1)

All participants will receive an informed consent form that explains the aims, courses, and potential benefits/risks of this study. They will be given no limit of time to read through it. The research team members will answer any questions regarding this study. Any research related activity will not be initiated unless they sign the consent form.

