The informed consent will be checked (the purpose of checking the consent is to assure that the subject is still interested in the study and they are still eligible to be in the study which will also be another form of an AE screening) along with a review of the medical history. Impressions of the subject upper and lower jaws will be taken with alginate for preparation of study models and surgical guides. Bite registration will be taken with a silicone material. Clinical measurements will be taken, including probing depth, gingival recession, plaque index, gingival index, keratinized mucosa width, and the PES score. A standardized peri-apical film will be taken along with clinical photos. Eligible subjects will be randomly assigned to one of the two groups after V3.

Implant and bone surgery (V4)

The informed consent will be checked along with a review of the medical history. The blood pressure and heart rate will be checked before surgery. The area selected for surgery will be locally anesthetized and examined. The hopeless tooth will be extracted under local anesthesia, without raising a flap. If necessary, a small flap might be elevated to facilitate the extraction. For subjects with intact buccal plate (equal or less than 4 mm loss), an implant will be placed according to the manufacturer's protocol for both groups. The implant position follows the computerized surgical guides (Neoguide, Neobiotech, South Korea) that are designed based on the CBCT scans. The gap between the implant and socket wall will be filled with bone allografts (The tooth root dimension is most of the time larger than the implant). In cases with a small buccal wall defect, a collagen membrane will be used. The test implants will be restored immediately with a provisional crown, which will be replaced by a permanent crown. A healing abutment and collatape to contain bone grafts

will be placed for control implants but without immediate restoration during the healing period. A removable temporary denture may be provided at subject request. All surgical procedures will be performed by a periodontist. Implant stability will be assessed at the time of placement. Any adverse events such as no implant stability, etc. during the surgery will be reported. Clinical measurements will be taken including: socket-related and implant-related parameters. A standardized peri-apical radiograph will be taken, as well as clinical photos.

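### A torque exclusion applied after randomisation is written for the test arm only, so the arms analysed need not be the arms randomised.

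*Combined protocol and SAP*

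**What the plan says.** **Timing of allocation.** The General Investigational Plan states "The subject will be randomly assigned before the surgery visit". The pre-implant visit (V3) text agrees: "Eligible subjects will be randomly assigned to one of the two groups after V3". Insertion torque is known only at V4.

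**The exclusion.** The paragraph on exclusions at V4 states "The test implant that does not achieve 30 N-cm will be treated as a control implant and excluded from the study". No 30 N-cm criterion for control implants appears anywhere in the document.

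**Rules that cover both arms.**
- Management of adverse events begins "If the dental implant does not achieve primary stability (10-20 % of prevalence rate) due to infection or other reasons", has the implant removed, and adds "The participants with the abovementioned conditions will be withdrawn from the study". No torque value is given.
- Patient selection lets a subject be a screen failure "up until the time that the implant is placed and deemed stable", followed by "All screen failed subjects will be replaced". It does not define stable.
- The only intraoperative exclusion criterion is "More than 4 mm of buccal plate dehiscence is present once the tooth is extracted".
- The Schedule of Events marks an eligibility screen at V4. Its V4 withdrawal cell lists only inadequate bone.

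**Analysis.** Section IV plans a repeated-measures analysis of variance between groups. It names no analysis set and does not say how randomised but excluded subjects are handled.

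**The concern.** The primary objective is a comparison between arms, and randomisation is what makes the arms comparable. Here a measurement taken after allocation decides who remains, in one arm only. Control implants in the same torque range meet no exclusion rule.

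If low-torque sites go on to worse recession or esthetics, the rule favours immediate restoration. If they do better, it favours delayed restoration. If torque is unrelated to outcome, or no implant falls in the band, there is no bias. The documents do not say which applies. If exclusion also ends follow-up, no later analysis can bring these subjects back.

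Their status is also unclear. They could be replaced screen failures, withdrawals or, on a less natural reading, subjects moved to the control pathway.

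**Working it through.** **1. Does the affected group exist on the plan's own terms?** Set the two V4 outcomes side by side. An implant without primary stability is removed and the subject is withdrawn, in either arm. A test implant below 30 N-cm is instead managed like a control implant, which implies that it stays in the mouth. The plan thus foresees implants that are retained but below 30 N-cm. The rules for both arms (dehiscence, lack of primary stability, later loosening or failure) carry no torque value, so a control implant in this band stays in. A replacement allocated to the test arm must again reach 30 N-cm, so replacement repeats the selection.

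**2. The plan's own sample size.** Inputs from Section IV: difference 0.8 mm, SD 0.8 mm (standardised difference 1.0), alpha 5% (taken as two-sided), power 80%, dropout 10%. The non-central t calculation gives 17 per arm (power 80.7%). 17/0.9 = 18.9, so 19 per arm or 38 in total, in line with the stated 40. With 20 randomised and 10% lost, 18 per arm gives 83.0%.

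**3. Chance that the rule is triggered.** The share f of implants stable but below 30 N-cm is not given; the 10-20% in the protocol refers to lack of primary stability. The chance that at least one of 20 test subjects is affected is 1 - (1 - f)^20:

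| f (assumed) | Chance |
|---|---|
| 1% | 18% |
| 5% | 64% |
| 10% | 88% |

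**4. Shift and type I error, illustration only.** Let pt and pc be the lowest-torque fractions lost in test and control, and r the torque-recession correlation. All three are assumed. With z_p the standard normal p-quantile and phi the standard normal density:

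shift = r × 0.8 × [phi(z_pt)/(1 - pt) - phi(z_pc)/(1 - pc)]

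For pt = 0.2, pc = 0.1: 0.280/0.8 - 0.1755/0.9 = 0.350 - 0.195 = 0.155. Multiplied by 0.8 and r, this gives 0.037 mm at r = 0.3 and 0.062 mm at r = 0.5. Type I error comes from simulation with no true effect (200,000 trials, 18 per arm, pooled t-test).

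| pc | pt | Shift, r = 0.3 / 0.5 (mm) | Type I error, r = 0.3 / 0.5 |
|---|---|---|---|
| 0.1 | 0.1 | 0 / 0 | about 5% |
| 0.1 | 0.2 | 0.037 / 0.062 | 5.2% / 5.6% |
| 0.1 | 0.3 | 0.072 / 0.121 | 5.8% / 7.5% |
| 0.2 | 0.2 | 0 / 0 | about 5% |
| 0.2 | 0.3 | 0.035 / 0.059 | 5.2% / 5.6% |
| 0 | 0.2 | 0.084 / 0.140 | 6.1% / 8.2% |
| 0 | 0.3 | 0.119 / 0.199 | 7.2% / 11.5% |

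The sign of the shift follows the sign of r. At r = 0 the shift is 0 and type I error is 5%.

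**5. Power, only if losses are not replaced.** With 10% dropout and 10% of controls also withdrawn, 20 × 0.9 × 0.9 = 16.2 controls remain. Test loss of 10%, 20% or 30% leaves 16.2, 14.4 or 12.6, with power 78.7%, 76.0% or 72.8%. In the first case both arms lose equally, so that drop is not due to the torque rule. The rule's own effect is the further fall of about 3 or 6 points. If the excluded subjects are replaced, this loss does not arise.

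**The case against.** The strongest counter-reading is that judging an implant stable, which ends the screening window in both arms, means reaching 30 N-cm in both arms. The exclusion would then be symmetric. The text does not rule this out, but nothing in it equates the two, and the torque sentence names only the test implant and has it retained rather than removed.

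The rule can also be read as a condition for delivering the test procedure, since the introduction ties immediate restoration to adequate primary stability. That explains the asymmetry without removing it.

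Two criticisms stand in part:
- The intraoperative criteria and the V4 withdrawal cell also omit lack of primary stability, so these lists are not exhaustive. Their silence on 30 N-cm is weak evidence about the status of these subjects.
- The size of the bias depends on chosen inputs. Another parameterisation, in which a share q of implants recedes by an extra g mm, gives a shift of q × g: 0.04 mm at 10% and 0.4 mm, up to 0.36 mm at 30% and 1.2 mm. With replacement, type I error is then 5.4% and 21.4%. None of these figures is a bound, and none should carry the severity.

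**Conclusion.** The concern holds. Followed as written, the plan filters one randomised arm and not the other on a measure taken after allocation. Neither replacement nor anything in Section IV repairs this. It should be fixed because a rule that breaks the randomised comparison by design is avoidable; no bias of a given size has been shown.

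The conclusion is conditional on at least one implant being stable but below 30 N-cm. Direction and size cannot be derived from the documents and may be zero. With at least 10% control loss assumed, the illustrated shift is at most 0.12 mm, or 15% of the 0.8 mm target. With no control loss it reaches 0.20 mm, or 25%. Confidence is high about what the rule says and does, and low about how much it would move the result.

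**What to change.** **Main change.** Open the allocation at V4 only after the implant is placed and the intraoperative eligibility and stability checks are recorded. Any exclusion the sponsor keeps is then decided blind to arm and applied alike to both arms. The V4 text describes the same extraction, placement and gap grafting for both groups up to the restoration step, so the stated question is unchanged.

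In the same amendment:
- Reconcile Patient selection, the V4 exclusion paragraph, Management of adverse events and the Schedule of Events on whether a test implant below 30 N-cm is a replaced screen failure, a withdrawal or a move to the control pathway. No torque threshold or restoration rule is proposed here.
- Name the analysis set in Section IV.
- Report all V4 exclusions, and all later withdrawals by arm, with reasons.

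**Cost.** A protocol amendment, allocation during surgery, and provisional-crown materials (and the temporary denture, where a subject might request one) ready in advance. If an exclusion is kept for both arms, results apply only to implants that pass it. Compared with a plan that already replaces test-arm exclusions, the extra number operated is 40/(1 - pt) - [20/(1 - pt) + 20/(1 - pc)]. With pt of 10-30% this is about 2-9 if no control is lost to the stability rule, and about 0-6 if that rule removes 10-20% of controls.

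**Fallback if allocation cannot be moved.** Keep following test subjects below 30 N-cm whose implant stays in place, with clinical handling as the protocol states, and analyse by randomised arm. State that this answers a treatment-strategy question, and state its power. If affected test subjects gain nothing and the others gain 0.8 mm (assumed), simulated power at 18 per arm falls to about 73% for a 10% share or 61% for a 20% share. Reaching 80% needs about 22 or 28 analysed per arm. Dividing by 0.9 gives 25 or 32 randomised per arm, which is 10 or 24 more than 40 in total. That allows for 10% dropout but not for stability withdrawals, and implants later removed as failed or loose are still lost. The fallback is clearly the weaker choice.
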